## 9.4 Retention of Investigational Product Vials

For this study, used and partially used drug vials will be retained for an adequate period to allow accountability by the CRA. No additional study drug samples will be retained.

#### 9.5 Allocation to Treatment

All potential participants who sign an informed consent at Screening will receive a unique 6-digit number (i.e. a Screening Number). The first 3 digits will represent the assigned site number and will be the same for each participant that screens at an individual site. The next 3 digits will be assigned sequentially (starting with 001). For patients who are deemed eligible, this 6-digit screening number will become the patient's permanent study ID number.

Eligible subjects in double-blind cohorts will be allocated a unique randomization number, in accordance with the randomization schedule. In each of NHV Cohorts 1-4, the first two subjects (sentinels) will be randomized separately to one active and one PBO. Each subject will be assigned to either active (ARO-HSD) or PBO treatment. The allocation of active treatment or PBO will be performed using a block randomization algorithm.

Participants who drop out prior to their EOS visit for reasons other than an adverse event, may be replaced.

## 9.6 Blinding and Code-Break

For blinded cohorts, blinding of study drug/PBO assignment is critical to the integrity of this clinical trial. It is expected that in most cases, AEs can be properly managed without the need for unblinding. However, in the event of a medical emergency in which knowledge of an individual participant's assignment is considered critical to the participant's well-being and management, the PI or documented designated treating physician may request permission to unblind the treatment assignment from the Arrowhead Pharmaceuticals, Inc. Medical Monitor. If the situation is not an immediate emergency, the PI should contact the responsible Medical Monitor to discuss the participant and circumstances requiring the unblinding. The blind will be broken only for the specific participant under discussion. Unblinding in situations that are not an immediate emergency may only take place with the notification and agreement of the responsible Medical Monitor. The randomization schedules will be maintained under controlled access. The personnel involved in the dispensing of investigational products will be accountable for ensuring compliance to randomization schedules. The non-blinded CRA will review the randomization schedule in comparison to the dispensing log to verify correct randomization.

If the PI considers an adverse event to be of such severity as to require immediate specific knowledge of the identity and dose of the relevant product, the treatment assignment can be determined by opening the code break envelope after discussion with the Medical Monitor and in the event of an absolute emergency. Only the Pharmacist and the PI will each have copies of the code break envelopes. The study monitor should also be informed promptly.

If a participant requires emergent unblinding (with or without a discussion between the Investigator and the Medical Monitor preceding the unblinding), the Investigator may also be required to complete a 'Drug Safety Unblinding Request/Notification Form' to document the medical rationale necessitating the unblinding. This form is then forwarded to the local Medical Monitor.

After the completion of the final study visit (not including 90-day follow-up phone call assessing compliance with contraception) for each cohort, unblinding for Sponsor analysis will occur at Sponsor discretion. After all subjects in double blinded cohorts have completed their EOS visit, all blinded cohorts may be unblinded.

Sponsor may request an interim descriptive analysis of the change from baseline in measured parameters any time after all NHV subjects planned for enrollment in each cohort have received at least one dose of ARO-HSD or PBO. This interim analysis is for planning of future studies and will not impact the conduct of this study. Sponsor will remain blinded to all subject treatment assignments. Descriptive statistics (that does not inadvertently unblind the trial) for change from baseline in pharmacodynamic measures will be calculated for all active subjects per cohort and for a pooled PBO group by an unblinded statistician and provided to Sponsor. For any AEs occurring more than once, the frequency of AEs for a specific preferred term will be calculated for pooled active and pooled PBO groups in such a way not to inadvertently break the subject-blind of the trial.

#### 10. STUDY METHODS AND SCHEDULES

#### 10.1 **Overview of Procedures**

Participants, who have consented to participate, had the screening examination and have met all of the protocol eligibility criteria will be randomized at a ratio of 4:4 (active:PBO) to receive a single subcutaneous injections of either PBO or ARO-HSD in double-blind fashion (for NHV Cohorts 1 through 4), or may receive open label ARO-HSD (Patient Cohorts 1b,3b and 4b). NHV Cohorts 1-4 will begin with administration of ARO-HSD or PBO to two sentinel participants (one ARO-HSD, one PBO). Following the Day 3 evaluation in these participants, if there are no significant safety concerns based on PI discretion, the remaining participants in the cohort may be treated.

During the study (according to the Schedule of Assessments listed in Tables 1-2), participants will undergo the following evaluations at regular intervals: medical history review, physical examinations, vital sign measurements (blood pressure, temperature, heart rate, and oxygen saturation, respiratory rate), weight measurement, AE monitoring, ECGs, urine pregnancy test (females of childbearing potential), and concomitant medication review. Blood samples will be collected for clinical laboratory analysis, and urine will be collected for urinalysis. Blood and urine samples will also be collected for pharmacokinetic and immunogenicity analysis. Patients in Cohorts 1b, 3b and 4b will have liver biopsies.

Participant visits to the clinical facility will occur as per the Schedule of Assessments. A telephone follow-up will occur 90 days after EOS to assess the patient's compliance with contraception requirements. Clinically significant changes including AEs will be followed until resolution is

achieved or considered medically stable. Refer to Schedule of Assessments (Tables 1-2) for additional information.

The PI (or medically qualified designee) will be required to remain within the clinical study facility for 2 hours after dosing on Day 1 and will remain on call for the duration of the study. Participants should refrain from strenuous physical activities throughout the study.

## 10.2 Selection and Screening

Prior to commencement of any screening procedures, the PI, or designee, will inform the participant about the nature and purpose of the study, including the risks and benefits involved, possible AEs, the fact that their participation is voluntary and provide a copy of the EC/IRB - approved Informed Consent Form for review. Each participant will acknowledge receipt of this information by giving written informed consent for their involvement in the study in the presence of the PI, or designee, who will also sign and date the Informed Consent Form. Time of consent will be recorded in the site's source documents and reflected in the eCRFs. The original signed consent form will be retained by the PI and a copy of the original will be given to the participant. Informed consent will be performed per the Principles of the International Conference on Harmonisation (ICH) Good Clinical Practice (cGCP) procedures.

Having given Informed Consent, potential participants will undergo procedures outlined in the Schedule of Assessments, to be performed within 60 days of the scheduled dosing date, to determine that they meet the inclusion/exclusion criteria specified in Sections 8.2 and 8.3.

# 10.3 On-Study Procedures/Assessments

## 10.3.1 Demographics/Medical History

Medical History will include previously diagnosed medical conditions, medication use over the previous 30 days, including vitamins, over-the-counter medications, prescription drugs, recreational drugs or supplements and alcohol and tobacco use.

## 10.3.2 Physical Exam

A complete physical exam will be performed at Screening. Areas examined include:

- Constitutional
- Skin
- HEENT
- Heart
- Lungs
- Back
- Abdomen
- Extremities
- Mental Status
- Neuro (gait/reflexes)
- Additional examination may be performed at investigator discretion

An abbreviated physical exam will be performed at pre-dose and EOS. Areas examined include:

- Constitutional
- Heart
- Lungs
- Abdomen
- Extremities
- Brief Neuro
- Additional examination may be performed at investigator discretion

At all other time points outlined in the Schedule of Assessments, a symptom-directed physical exam will be performed as needed. Height (during screening, in centimeters, without shoes) and weight (kilograms, without shoes) should be recorded to determine BMI where specified in SOA.

# 10.3.3 Electrocardiogram

A single 12-lead ECG measurement will be obtained at time points outlined in the Schedule of Assessments after the participant is semi-supine for at least 3 minutes. On dosing days ECGs will be performed pre-dose and 1 and 2 hours post-dose and may be performed more frequently if indicated. ECGs should be performed within a window of 10 minutes, prior to other invasive procedures such as blood draws. Any abnormal ECGs will be repeated in triplicate, with each measurement approximately 1 minute apart. Only abnormal ECG readings that are considered clinically significant in the opinion of the investigator need to be repeated in triplicate. Triplicate ECGs are three tracings approximately 1 minute apart. If the originally scheduled ECG is considered clinically significant, both the first tracing and the triplicate tracings will be entered into the EDC.

## **10.3.4 Vital Sign Assessments**

Systolic/diastolic blood pressure, temperature, heart rate, respiratory rate (breaths/min) and oxygen levels will be obtained at time points outlined in the Schedule of Assessments after the participant is semi-supine for at least 3 minutes. Vitals signs will be obtained prior to venipuncture and other invasive procedures.

# **10.3.5 Clinical Laboratory Tests**

Blood and urine samples will be collected to perform clinical laboratory tests. Participants will be required to fast for the screening and other pharmacodynamic sample collections.

Central labs will be utilized. However, local labs may be utilized as necessary if needed by the investigator or for emergent situations.

Within the screen period, up to 60 days prior to the first dose of study medication, a blood and urine sample will be collected for the laboratory tests detailed below to establish baseline data and eligibility for enrolment. One repeat Screening lab draw is allowed per assessment to

establish eligibility. The results will be assessed by the PI, or medically qualified designee, before study enrollment. Any abnormality in laboratory values (that are confirmed on repeat) deemed clinically significant by the PI, or medically qualified designee (i.e., those that would jeopardize the safety of the participant or impact on the validity of the study results), will result in exclusion of that participant. Clinical laboratory tests will be performed on participants' blood and urine at specified time-points listed in the Schedule of Assessments.

- *Biochemistry*: Sodium, potassium, chloride, bicarbonate, glucose, urea, creatinine (including calculated creatinine clearance), creatine kinase, phosphate, total calcium, albumin, total protein, total bilirubin, lipase and amylase, conjugated bilirubin, alkaline phosphatase (ALP), alanine aminotransferase (ALT), and aspartate transaminase (AST), hemoglobin A1C
- *Hematology:* Hemoglobin, red blood cell count (RBC), hematocrit, mean cell volume (MCV), mean cell hemoglobin (MCH), mean cell hemoglobin concentration (MCHC), platelets, white cell count, neutrophils, lymphocytes, monocytes, eosinophils and basophils
- Coagulation: Partial thromboplastin time (PTT), Prothrombin time (PT) with INR
- *Urinalysis:* Leucocytes, nitrites, urobilinogen, protein, pH, blood, specific gravity, ketone, bilirubin and glucose
- *Urine drug screen:* urine will be analyzed for benzodiazepines, amphetamines, methamphetamines, methadone, phencyclidine, barbiturates, opiates, cocaine, ecstasy and cannabinoids
- *Microscopic urinalysis will be performed if indicated:* white blood cells, red blood cells, epithelial cells, bacteria
- *Serology:* Hepatitis B surface antigen, Hepatitis C antibody and HIV antibody screen. If necessary, participants will be counseled by the PI, or medically trained designee, concerning the blood tests for Hepatitis B surface antigen, Hepatitis C and HIV antibodies, and their subsequent results.
- *FSH*: Post-menopausal status will be confirmed by follicle-stimulating hormone (FSH) level consistent with post-menopausal state.
- *Pregnancy:* Females of childbearing potential will have a urine pregnancy test at Screening and pre-dose on dosing days and biopsy days. If urine pregnancy test is positive, dosing or biopsy should not occur, and the patient will be referred to their primary care provider for follow up.
- *Lipid Parameters:* LDL-C, total cholesterol, non-HDL-C, HDL-C, VLDL-C, and triglycerides
- Retinoid pathway markers: retinol, retinol binding protein

- *NASH biomarkers*: ELF [Hyaluronic acid (HA), Procollagen III amino terminal peptide (PIIINP), Tissue inhibitor of metalloproteinase 1 (TIMP-1)], cytokeratin-18, PRO-C3, IL-1β, IL-6, IL-10, INF-gamma, and TNF-α
- *Immunogenicity:* Specified subjects will be assessed for anti-drug antibodies.
- *Genotype:* All patient cohorts will be assessed for HSD17βB13 and PNPLA3 gene variants with the subject's written consent.
- **Exosomal analysis:** blood will be drawn for exosomal analysis of *PNPLA3* and *HSD17B13* if technically feasible.

The Day 1 (pre-dose) value will be used as each participant's baseline value for data analysis purposes or as otherwise specified. If Day 1 or as otherwise specified values are erroneous or not available and repeat blood draw is not possible, the pre-dose value closest to Day 1 (e.g., Screening) may be used as baseline.

# 10.3.6 Hepatic Imaging (only for patient Cohorts 1b, 3b and 4b)

Patients must fast from food for at least 4 hours prior to MRI.

Magnetic Resonance Imaging: Liver fat content via MRI-PDFF will be evaluated and quantified per the Schedule of Assessments. MRI reading for eligibility and post-dose will be completed centrally.

FibroScan®: Per the Schedule of Assessments, pre-dose and post-dose liver stiffness will be evaluated using FibroScan® standard procedures. No centralized reading is required for FibroScan. An equivalent ultrasound elastography method may be used.

Please see separate imaging manual for specific instructions related to hepatic MRI.

# 10.3.7 Liver Biopsy (only for Cohorts 1b, 3b and 4b)

With training and Sponsor approval, only those sites capable of processing biopsy tissue in accordance with the Laboratory and Biopsy Manuals will be required to obtain samples for protein expression analysis at the time points outlined in the Schedule of Assessments.

Samples will be used to assess effect of treatment on:

- HSD17B13 mRNA and PNPLA3 mRNA.
- Protein expression for HSD17B13 and PNPLA3 (if scientifically feasible).

The liver biopsy procedure and D1 dosing can be done on the same date. The only requirement is for the liver biopsy procedure to be completed before any other D1 procedures, especially dosing.

If the patient agrees to an additional biopsy core during Screening to confirm NASH diagnosis, the histopathology can be conducted as an option by the sites and histopathology costs will be covered by the Sponsor. This optional procedure should not be used to confirm patient eligibility.

Please see separate laboratory and biopsy manuals for specific instructions related to biopsy performance.

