BMI (Height and Body Weight)	X	$X^1$							$\mathbf{X}^{1}$		$X^1$		$X^1$	
Concomitant Meds/Therapies	X	X					X	X	X	X	X	X	X	
Electrocardiogram (See Section 10.3.3)	X	X			X	X	X		$(0, 1, 2hr)^2$				X	
Urine Pregnancy Test (WOCP) confirmed negative pre-dose/pre-bx	X	X							pre-dose		pre-bx		X	
FSH (post-menopause)	X													
Urine Drug Screen	X													
Vitals (BP, temp, HR, RR, O 2 )	X	X		X	X	X	X	X	X	X	X	X	X	
HIV, Hep B, C	X													
Labs (heme, coag, chem, lipase, lipids)	X	X					X	X	X	X	X	X	X	
Retinol, RBP, blood for exosomes, cytokine panel		X						X	X	X	X	X	X	
Hemoglobin A1c	X	X											X	
Pro-C3, ELF, Cytokeratin-18		X											X	
Blood PK		X		X	X	X	X	X	pre-dose					
Genotyping (HSD17β13, PNPLA3)	X													
Urinalysis	X	X					X	X	X	X	X	X	X	
Liver Biopsy, FibroScan, MRI-PDFF	X 										X			
Administration of ARO-HSD			X						X					

<sup>1 Body weight only  10-minute window allowed

<sup>3 Liver biopsy can be done at D1, as long it is completed prior to any D1 procedures Version 7.0, 12 March 2021

Arrowhead Pharmaceuticals, Inc. Protocol No.: AROHSD1001

Confidential

Page 11 of 59

Anti-Drug Antibodies		X				X		X	
Adverse Events Collection	х –							X	
Pregnancy phone call									X

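### For a Day 1 liver biopsy, the biopsy-first rule contradicts the requirement for a negative pregnancy test before biopsy; a minor side effect is a same-day post-biopsy baseline for 7 exploratory blood-marker endpoints

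*Protocol*

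**What the plan says.** Table 2 of the Protocol places the first biopsy in the Screening column (Day -60 to Day -1), but footnote 3 adds an option: "Liver biopsy can be done at D1, as long it is completed prior to any D1 procedures". Section 10.3.7 repeats the option in the text: "The only requirement is for the liver biopsy procedure to be completed before any other D1 procedures, especially dosing".

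On pregnancy testing, 10.3.5 calls for a urine test in women of childbearing potential at Screening, before dosing on dosing days, and on biopsy days. It then says: "If urine pregnancy test is positive, dosing or biopsy should not occur". The Table 2 row is labelled "Urine Pregnancy Test (WOCP) confirmed negative pre-dose/pre-bx" and is marked at Screening, Day 1 pre-dose, Day 29 pre-dose, Day 71 before biopsy, and EOS.

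On marker baselines, 10.3.5 says "The Day 1 (pre-dose) value will be used as each" participant's baseline, with the closest earlier pre-dose value as a fallback. SAP Section 5 uses the last non-missing value before the first dose. In Table 2, the rows "Retinol, RBP, blood for exosomes, cytokine panel" and "Pro-C3, ELF, Cytokeratin-18" are blank at Screening and start at Day 1 pre-dose.

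**The concern.** The Day 1 pregnancy test is a Day 1 procedure. If the biopsy must be finished before every other Day 1 procedure, the test comes after it and cannot stop it. A site that tests first breaks 10.3.7 and footnote 3. A site that takes the biopsy first defeats the purpose of 10.3.5. Under 13.8, any noncompliance with protocol requirements is a deviation, so either order counts as one. What is at stake is an invasive procedure in a woman of childbearing potential before the same-day check meant to prevent it.

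The second effect is statistical and smaller. The same rule moves the Day 1 pre-dose marker draw to just after the biopsy, and that draw is the baseline. SAP 9.7.2 reports change and percent change from baseline in open-label, all-active cohorts of up to 6. If a biopsy shifted a marker for a few hours, these patients would have no control arm against which to see it.

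**Working it through.** No stated figure is in question. The check sets the rules side by side and counts the endpoints.

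**Pregnancy test on a Day 1 biopsy**

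1. Order under 10.3.7 and footnote 3: biopsy, then all other Day 1 procedures.
2. Status of the test: Table 2 marks it in the Day 1 pre-dose column, so it is one of those other procedures.
3. Order under 10.3.5 and the Table 2 row label: negative test, then biopsy.
4. Steps 1 and 3 cannot both hold. On Day 71 the same row is marked explicitly as before biopsy, so the intended order is clear. Day 1 alone carries a rule that reverses it.
5. The Screening test does not fill the gap well. Screening procedures are "to be performed within 60 days of the scheduled dosing date", so it can be up to 60 days old.
6. In either order the Day 1 test still precedes dosing, so drug exposure is not in question.

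**Marker baselines**

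1. Protocol 6.3 lists 13 patient-cohort exploratory endpoints. Four are biopsy-derived, one is MRI-PDFF, and one (ALT/AST) has a Screening sample.
2. 13 - 4 - 1 - 1 = 7 have Day 1 pre-dose as their first sample: CK-18, the cytokine panel, retinol/RBP, exosomal HSD17B13 mRNA, exosomal PNPLA3 mRNA, ELF and Pro-C3.
3. Three of the 7 (CK-18, ELF, Pro-C3) have one later value, at EOS. The other 4 have six later values: Days 15, 29, 57, 71, 85 and 113.
4. SAP 9.7.2 names markers for 5 of the 7. It does not name the two exosomal mRNAs, which the protocol makes conditional on feasibility.
5. Interval from biopsy to baseline draw: 1 to 60 days for a Screening biopsy (Day -1 to Day -60), and the same day for a Day 1 biopsy. In both cases the baseline follows the biopsy.

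**Patients**

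- Planned: 3 x 6 = 18. With two extra allowed in each of 1b and 3b: 8 + 8 + 6 = 22.
- Cohort 1b enrolls after 3b and 4b, so a new order mainly helps up to 6 patients, or 6 + 2 = 8.
- The number using the Day 1 option is not given; it could be none or all.

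**The case against.** The strongest reply is that the specific safety rule governs the general sequencing sentence. 10.3.5 requires a test on biopsy days, the Table 2 label requires it to be negative before biopsy, and the end of the 10.3.7 sentence shows that its aim is an undosed baseline biopsy. A sensible site would treat the test as biopsy preparation. The laboratory and biopsy manuals, which are not among the documents, may say so. This limits the practical risk but does not remove the contradiction: 10.3.7 calls its order the sole requirement, and a manual that put the test first would conflict with the protocol.

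A reader might infer that the Screening test is the last one required before a Day 1 biopsy. The documents do not support that, because 10.3.5 and the Table 2 label separately require a test before biopsy on the biopsy day. The defect is a conflict between rules, not a missing rule.

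A reader might also infer that the Day 1 option deprives patients of a pre-biopsy marker sample that others have. It does not. Table 2 draws these markers first at Day 1 pre-dose for everyone, so patients biopsied in Screening lack one too. The general Screening sentence in 10.3.5 does not change this, because the same section ties sampling times to the Schedule of Assessments, where the Screening cells are blank.

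Finally, a reader might infer a bias of some size in the marker results. No document says that biopsy moves these markers, in which direction, or by how much. The endpoints are exploratory and SAP 2.2 tests no formal hypotheses.

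**Conclusion.** The contradiction on the pregnancy test stands. For Day 1 biopsies, the protocol gives two orders that cannot both be followed, on a participant-safety check. It reaches only women of childbearing potential who use the Day 1 option, among at most 22 patients; their number is unknown.

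The marker point stands only as a secondary remark. For Day 1 users, the baseline of 7 of 13 exploratory endpoints is a same-day post-biopsy draw, against 1 to 60 days after biopsy for the others. Whether that shorter interval matters is unknown, and the effect may be zero. The primary AE endpoint and the biopsy mRNA comparison are not affected, and no bias in ALT or AST is claimed. The priority is minor, and the change is worth making because it is cheap.

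**What to change.** Amend 10.3.7 and Table 2 footnote 3 to state the order for a same-day biopsy:

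1. Urine pregnancy test confirmed negative (women of childbearing potential), and the already planned marker bloods drawn (retinol/RBP, exosomes, cytokines, Pro-C3, ELF, CK-18). Both may fall outside the 2-hour pre-dose window if needed.
2. Biopsy completed.
3. Remaining pre-dose procedures (safety labs, PK, anti-drug antibodies, vital signs, ECG), which may follow the biopsy.
4. Dosing.

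The baseline rule in SAP Section 5 then selects the pre-biopsy marker sample without a change. For Day 1 biopsies, the number of these endpoints with a post-biopsy baseline falls from 7 to 0; for Screening biopsies nothing changes. Optionally, the SAP could list the interval from biopsy to baseline marker draw for all patients. That is better than flagging only Day 1 biopsies, because a biopsy on Day -1 raises nearly the same question. Procedure times are recorded in the CRF (10.6), so the listing is feasible.

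Costs: a short amendment with EC/IRB approval (13.2); a pre-dose blood draw split in two for these patients; and a stay longer than the planned 2 hours before dosing. Marker baselines would also be pre-biopsy for some patients and post-biopsy for others within a small cohort. No test or visit is added. Patients already dosed cannot benefit from the new order; for them only the listing applies.
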